NON-INTERVENTIONAL POST-AUTHORISATION SAFETY STUDY (PASS) PROTOCOL

COMPOUND: STAMARIL®

Effectiveness evaluation of the local additional risk minimisation measures for STAMARIL® in the United Kingdom: a survey for healthcare professionals and vaccinees

STUDY NUMBER: STA00059

The Study is condu	acted by Sanofi/IQVIA hereinafter refo	erred also as the "MAH/MAH representative	···.
Version Number:	3.0		
Date:	31 May 2023	Total number of pages:	86

Any and all information presented in this document shall be treated as confidential. The use of such confidential information must be restricted to the recipient for the agreed purpose and must not be disclosed, published or otherwise communicated to any unauthorized persons, for any reasons, in any form whatsoever without the prior written consent of MAH/MAH representative

According to template: QSD-011626 VERSION N°7.0 (23-JUL-2020)

NAMES AND ADDRESSES OF

COUNTRY TEAM'S REPRESENTATIVE

Name: Address:

Tel: Fax: Email:

MAH/MAH REPRESENTATIVE MAH/MAH representative: Address:

SANOFI PASTEUR S.A. [name]

PASS Information

Title	Effectiveness evaluation of the local additional risk minimisation measures for STAMARIL® in the United Kingdom: a survey for healthcare professionals and vaccinees	
Protocol version identifier	3.0	
Date of last version of protocol	10 October 2022	
EU PAS register number	EUPAS50782	
Active substance	Yellow fever virus, 17D-204 strain (live, attenuated)	
Medicinal product	STAMARIL®	
Product reference	PL 46602/0007	
Procedure number	DE/H/0476/001	
Marketing authorisation holder(s)	Sanofi Pasteur	
Joint PASS	No	
Research question and objectives	Primary objectives:	
	1. To measure:	
	a. Awareness of the UK (STAMARIL®) yellow fever pre- vaccination checklist by qualified healthcare professionals (HCPs) of designated authorised yellow fever vaccination centres (YFVCs) in the UK	
	b. Utilisation of any standardised yellow fever pre-vaccination checklist(s) by qualified HCPs of designated authorised YFVCs in the UK	
	c. Distribution of the STAMARIL® Patient Information Leaflet (PIL) by qualified HCPs of designated authorised YFVCs to yellow fever vaccinees in the UK	
	2. To evaluate knowledge and understanding of the key safety messages associated with yellow fever vaccination in any standardised yellow fever pre-vaccination checklist(s) among qualified HCPs of designated authorised YFVCs in the UK.	
	3. To verify the receipt of the STAMARIL® PIL by yellow fever vaccinees at the time they get vaccination consultation in the UK.	
	Secondary objective: None	
	1.	
Country of study	United Kingdom	
Authors		

Marketing authorisation holder(s)

Marketing authorisation holder(s)	SANOFI PASTEUR S.A. [name]
MAH/MAH REPRESENTATIVE contact person	

2 LIST OF ABBREVIATIONS

AE adverse event

aRMMs additional risk minimisation measures

CI confidence interval

EDC electronic data capture

EMA European medicines agency

ENCePP European network of centres for pharmacoepidemiology and pharmacovigilance

EphMRA European pharmaceutical Marketing Research Association

GVP good pharmacovigilance practices

HCP healthcare professional

HPS Health Protection Scotland

ICVP international certificate of vaccination or prophylaxis

IEC institutional ethics committee

IHR international health regulations

IRB institutional review board

MAH Marketing authorisation holder

MHRA Medicines and Healthcare products Regulatory Agency

NaTHNaC National Travel Health Network and Centre

PASS Post-authorisation safety study

PGD patient group direction
PHS Public Health Scotland

PIL patient information leaflet

QMS quality management system

SAE serious adverse event
SAP statistical analysis plan

SOP standard operating procedure

SmPC summary of product characteristics

STROBE Strengthening the Reporting of Observational Studies in Epidemiology

UK United Kingdom

YFVCs yellow fever vaccination centres

4 ABSTRACT

Title: Effectiveness evaluation of the local additional risk minimisation measures for STAMARIL® in the United Kingdom: a survey for healthcare professionals and vaccinees

Rationale and background:

STAMARIL[®] is a live attenuated yellow fever 17D-204 strain vaccine which is prepared by culturing the virus in embryonated eggs. It is indicated for active immunisation against yellow fever caused by yellow fever virus in people over 9-months of age who are travelling to or living in areas or countries with a risk of yellow fever transmission, as well as laboratory workers handling potentially infectious materials.

Sanofi Pasteur is the only marketing authorisation holder (MAH) for yellow fever vaccine (STAMARIL®) in the United Kingdom (UK). Following two fatal adverse reactions to yellow fever vaccine in the UK in 2018-2019, due to unapproved use in both cases, the UK Medicines and Healthcare products Regulatory Agency (MHRA) requested the MAH to add a standardised UK checklist, developed by MHRA (hereby referred to as 'UK (STAMARIL®) yellow fever prevaccination checklist' in this protocol), as part of the local additional risk minimisation measures (aRMMs) in the STAMARIL[®] Risk Management Plan, to support the UK healthcare professionals (HCPs) in the benefit-risk assessment process. The objective of this checklist is to ensure compliance of HCPs of designated authorised yellow fever vaccination centres (YFVCs) with indications, contraindications, warnings, and precautions as per the Summary of Product Characteristics (SmPC) and to support the appropriate evaluation of individual risk-benefit balance. The most recent SmPC (dated 15 Feb 2021) details the consideration of risk-benefit balance for individual travellers. In addition to the UK (STAMARIL®) yellow fever prevaccination checklist, another yellow fever pre-vaccination checklist has been issued by the National Travel Health Network and Centre (NaTHNaC)/ Public Health Scotland (PHS) which is intended for vaccinees (travellers) to read and complete in advance of, or during, the travel health consultation; it is also commonly called the 'traveller's checklist'. Because the contents of both these checklists (i.e. UK (STAMARIL®) yellow fever pre-vaccination checklist and NaTHNaC/PHS yellow fever pre-vaccination checklist) are similar, 'standardised yellow fever pre-vaccination checklist(s)' refers to either or both of these checklists throughout this protocol.

Furthermore, a patient information leaflet (PIL) should be provided by HCPs to each yellow fever vaccinee which was amended in line with the revisions of the most recent SmPC (dated 15 Feb 2021).

The MAH is also asked to evaluate the effectiveness of implementation of the UK checklist and PIL. Therefore, this post-authorisation safety study (PASS) survey is designed to assess the effectiveness of the UK (STAMARIL®) yellow fever pre-vaccination checklist among the qualified HCPs of designated authorised YFVCs. In addition, this survey will also assess the effectiveness of the the STAMARIL® PIL among yellow fever vaccinees (or their parents/guardians if vaccinees are younger than 18 years old) in the UK.

31-May-2023 Version number: 3.0

Research question and objectives:

The aim of the current study is to examine the effectiveness of the UK (STAMARIL®) yellow fever pre-vaccination checklist among qualified HCPs of designated authorised YFVCs and of the STAMARIL® PIL among yellow fever vaccinees in the UK, by conducting a survey in this population.

The primary objectives of this study are:

1. To measure:

- a. Awareness of the UK (STAMARIL®) yellow fever pre-vaccination checklist by qualified HCPs of designated authorised YFVCs in the UK.
- b. Utilisation of any standardised yellow fever pre-vaccination checklist(s) by qualified HCPs of designated authorised YFVCs in the UK.
- c. Distribution of the STAMARIL® PIL by qualified HCPs of designated authorised YFVCs to yellow fever vaccinees in the UK.
- 2. To evaluate knowledge and understanding of the key safety messages associated with yellow fever vaccination in any standardised yellow fever pre-vaccination checklist(s) among qualified HCPs of designated authorised YFVCs in the UK.
- 3. To verify the receipt of the STAMARIL® PIL by yellow fever vaccinees at the time they get vaccination consultation in the UK.

There is no secondary objective. **Study design:**

This will be a national, multicentre, prospective, cross-sectional, and multi-channel survey based on primary data collection conducted separately among qualified HCPs (physicians, nurses and pharmacists) and STAMARIL® vaccinees (or their parents/guardians if vaccinees are younger than 18 years old) in the UK (England, Wales, Northern Ireland and Scotland). The survey will be conducted primarily through a web (and/or paper for vaccinees) questionnaire. The survey will be conducted within 12 to 18 months following the implementation of the local aRMM in the UK as per the European guideline on good pharmacovigilance practices (GVP) – Module XVI (Rev 3).

Population:

The target population of the survey will be qualified HCPs (physicians, nurses and pharmacists) providing consultation for yellow fever vaccine administration and/or administering yellow fever vaccine (STAMARIL®), and yellow fever vaccinees (or their parents/guardians if vaccinees are younger than 18 years old) in the UK. Based on the NaTHNaC Annual Return 2020 report, there were a total of 2,295 YFVCs that remained designated in 2020 in England, Wales, and Northern Ireland. Based on the information provided on PHS website, as of January 2022, there are 123 YFVCs in Scotland.

Inclusion criteria

The following criteria must be met in order to be enrolled in the study:

31-May-2023

Version number: 3.0

- 1. For HCPs: Qualified HCPs from designated authorised YFVCs who have provided consultation for yellow fever vaccine administration and/or administered yellow fever vaccines in the UK in the past 12 months and are willing to consent to participate in the survey. A qualified HCP refers to the one who has undertaken the yellow fever training programme, sponsored by the NaTHNaC or PHS during the past 24 months.
- 2. For vaccinees: Individuals who receive yellow fever vaccine in the UK and are willing to consent (or their parents/guardians if individuals are younger than 18 years old) to participate in the survey.

Exclusion criteria

Individuals meeting any of the following criteria are not eligible for participation:

1. For HCPs:

- a. Who declare having a conflict of interest with the survey (i.e., HCPs employed by regulatory bodies, or pharmaceutical industries etc).
- b. Who are unable or not willing to provide voluntary consent to participate in this survey conducted in the UK.
- c. Who are not qualified to provide consultation for yellow fever vaccine administration and/or administer yellow fever vaccines in the UK (i.e., HCPs who have not undertaken yellow fever training sponsored by the NaTHNaC or PHS in the past 24 months).
- 2. For vaccinees (or their parents/guardians if vaccinees are younger than 18 years old):
 - a. Who declare having a conflict of interest with the survey (i.e., employed by regulatory bodies, or pharmaceutical industries etc., or are immediate family of qualified HCP's of designated authorised YFVCs or are employed by YFVCs).
 - b. Who are unable or not willing to provide voluntary consent to participate in this survey conducted in the UK.

Variables:

HCP questionnaire

The following variables will be collected through the HCP survey:

- Variables related to HCPs' practice:
 - o Demographic information (age range, gender and region)
 - HCP profession (physician, nurse or pharmacist)
 - Type of work setting (General Practice [National Health Service], General Practice [Private], pharmacy, travel clinic, occupational health department, hospital, or other)
 - Years of experience in the profession

- 31-May-2023 Version number: 3.0
- o Prescriber administering STAMARIL® against a Patient Group Direction (PGD)¹
- Experience with STAMARIL[®] (whether providing consultation and/or administering STAMARIL[®], years of experience in providing consultation and/or administering STAMARIL[®] and number of patients administered with STAMARIL[®] and/or provided consultation for the administration of STAMARIL[®] in the past 12 months)
- Yellow fever training sponsored by NaTHNaC or PHS (HCP trained ≤12 months ago or >12 months ago)
- Variables related to the HCPs awareness, utilisation, and distribution of the aRMM materials:
 - Awareness of the UK (STAMARIL®) yellow fever pre-vaccination checklist by the HCPs
 - o Use of the UK (STAMARIL®) yellow fever pre-vaccination checklist by the HCPs
 - O Use of the NaTHNaC/PHS yellow fever pre-vaccination checklist² by the HCPs
 - O Distribution of STAMARIL® PIL by the HCPs to yellow fever vaccinees
- Variables related to the knowledge and understanding of the key safety messages in any standardised yellow fever pre-vaccination checklist(s)
 - Indications (e.g. yellow fever activity at travel destination) and contraindications (e.g. hypersensitivity to vaccine components, immunosuppression [congenital or acquired], thymus dysfunction, thymoma, thymectomy, or age less than 6-months), or precautions (e.g. infants from 6 up to 9 months of age, advanced age, pregnancies and breastfeeding)
 - Possible side effects (including signs and symptoms of yellow fever vaccine-associated viscerotropic disease and yellow fever vaccine-associated neurotropic disease, hypersensitivity)

Vaccinee questionnaire

_

¹ Patient Group Directions (PGDs) provide a legal framework that allows some registered HCPs to supply and/or administer specified medicines to a pre-defined group of patients, without them having to see a prescriber (such as a doctor or nurse prescriber)

² Note: In addition to the checklist developed by MHRA, NaTHNaC/PHS has also issued a checklist which aligns with the Green Book (the Green Book has the latest information on vaccines and vaccination procedures for all the vaccine preventable infectious diseases that may occur in the UK) and is intended for travellers to read and complete for yellow fever consultation with HCPs; both checklists are similar in content.

The following variables will be collected through the vaccinee survey:

- Variables related to vaccinees' demographic information (age range, gender, region and education level)
- Variables related to vaccinee's receipt of the STAMARIL® PIL.

Data sources:

The survey is a primary data collection conducted through two questionnaires (HCP and vaccinee) administered mainly by web; paper will be a supplement to web for vaccinee questionnaire. It is estimated to take 10 to 15 minutes to complete HCP questionnaire, and up to 5 minutes to complete vaccinee questionnaire.

Study size:

Considering an expected proportion of interest of 50% (the most conservative), approximately 300 completed questionnaires per target population (300 HCPs and 300 vaccinees)³ will be ideal goal, providing a precision of 5.7% for confidence interval (CI) of 95%.

Due to COVID-19 pandemic, the feasibility assessment will be done close to the start of fieldwork to predict the likelihood of achieving the desired sample size. For this survey, a minimum sample size of 200 HCPs (a 7% precision) and 150 vaccinees (an 8% precision) will be targeted assuming an expected proportion of interest of 50%. However, if the minimal sample size is not achieved within the allocated fieldwork timelines, the data collection will then be stopped and the study report will be written and submitted based on the analysis of all available data.

Data analysis:

The statistical analysis will be conducted using the SAS® software V9.4 (SAS Institute, North Carolina, USA) or R version 3.6 or higher on WindowsTM. All the analyses will be descriptive. Continuous variables will be described by their number (of valid cases, of missing values), mean, standard deviation, and median, Q1, Q3, minimum and maximum. Categorical variables will be described as the total number and relative percentage per category.

In case of multiple-choice questions, the frequency of each option provided by the HCPs/vaccinees will be reported as the total number and relative percentage per category. Different combinations of the answers provided (if any) will not be considered.

Wilson CI of 95% will be evaluated on the overall result.

The participation rate will be analysed overall and per region for HCPs and vaccinees separately.

The proportions of correct and desirable answers to the selected questions asked in the questionnaire will be separately expressed for HCPs and vaccinees (or their parents/guardians if

³ In the years following the COVID-19 pandemic these numbers may drop due to the reduced frequency of travelling

vaccinees are younger than 18 years old) who provide answers to those questions (missing data will not be counted as a denominator in proportions). Success indicators by objectives will be presented separately for HCPs and vaccinees.

In the first step, calculations will be performed overall and per region on raw data. In the second step, only overall results will be weighted according to the proportion of HCPs and vaccinees in each region in order to accurately reflect the population that the survey seeks to measure. Estimation of the HCP universe will be determined using the number of YFVCs in each region and median of qualified HCPs in YFVCs based on the official websites (https://nathnacyfzone.org.uk and https://www.hps.scot.nhs.uk/a-to-z-of-topics/yellow-fever-vaccination-centres/find-a-yellow-fever-vaccination-centre). For vaccinees, an approximation of vaccinees universe will be obtained from the vaccine sales data of each region, provided by the MAH.

The statistical results will be presented in the same report, as overall and per region for both the questionnaires.

Milestones:

The data collection is planned to start in March-April 2023 and end in August-September 2023. The final study report will be submitted in January-February 2024.

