To evaluate knowledge and understanding The proportion of qualified HCPs who of the key safety messages associated with provide desirable responses for each yellow fever vaccination in any question related to knowledge and standardised yellow fever pre-vaccination understanding of key safety messages. checklist(s) among qualified HCPs of Success indicator for knowledge and designated authorised YFVCs in the UK. understanding: If ≥80% of qualified HCPs are successful (a qualified HCP is considered successful when he/she provides at least 80% of desirable responses to questions related to knowledge and understanding). To verify the receipt of the STAMARIL® a. The proportion of yellow fever vaccinees who receive the STAMARIL® PIL by yellow fever vaccinees at the time they get vaccination consultation in the UK. PIL Success indicator for receipt of STAMARIL® PIL: If >80% of vaccinees are successful (a vaccinee is considered successful when he/she receives the STAMARIL® PIL). Secondary objective: None

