9.5 STUDY SIZE

9.5.1 Determination of sample size

The sample size formula based on the normal approximation of the binomial distribution, for calculating the number of participants required for a proportion is as follows:

$$n = \frac{P \cdot (1-P) \cdot \left(Z_{1-\alpha/2}\right)^2}{e^2},$$

where P is the expected proportion, e is one half the desired width of the confidence interval (CI), and $Z_{1-\alpha/2}$ is the standard normal Z value corresponding to a cumulative probability of $1-\alpha/2$ (e.g., if α =.05 then Z = 1.96). The following table provides the margin of error for 95% CI based on various sample sizes and proportions of interest.

Table 2 Margin of error for 95% CI based on various sample sizes and proportions of interest

Margin of error for 95% CI (absolute precision)							
Proportion of interest	8%	7%	5.7%	5%	4%		
10%	54	71	106	139	216		
30%	126	165	248	323	504		
50%	150	196	295	384	600		
70%	126	165	248	323	504		
90%	54	71	106	139	216		

As P is not known in advance, we consider it to be 50%. Such a hypothesis yields the most conservative i.e. the largest, sample size.

Based on 2019 figures,²³ a minimum sample size of 200 HCPs (a 7% precision) and 150 vaccinees (a 8% precision) are targeted assuming an expected proportion of interest of 50%. If the proportion of interest is greater than 50% which may be predicted from other sources such as an Annual Return Report, the precision could be further increased with the same sample size, or the sample size could be further decreased with the same precision. For example, based on the Annual Return 2020 report published by NaTHNaC, 90.7% of YFVCs supplied the yellow fever vaccine PIL routinely to travellers receiving yellow fever vaccination. In this case, a sample size of 200 HCPs will achieve a precision below 4%. If a similar proportion of vaccinees (or parents/guardians of minor vaccinees) can also confirm receipt of yellow fever vaccine PIL, a sample size of 54 vaccinees will achieve an 8% precision in this case.

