The questions considered as complementary will not be included in the assessment of success. The details of the assessment of the success for each survey and each objective is described in Annex 6.

Success at the HCP/vaccinee level will be defined for each primary objective based on the number of sub-questions related to that objective being completed with desirable responses. A HCP/vaccinee will be successful in each objective (except knowledge and understanding for HCPs) if all related questions, including sub-questions, will be completed with desirable responses (Annex 6). An HCP will be successful for knowledge and understanding of any standardised yellow fever pre-vaccination checklist(s), if at least 80% of the related questions, including sub-questions, are completed with desirable responses.

A threshold of 80% successful HCPs or vaccinees on each of the primary outcomes would be considered appropriate for assessing the effectiveness of an aRMM.

It should be noted that the selection of this threshold for success is subjective and not based on *a priori* knowledge, experience, or established scientific criteria in the education or risk communication or evaluation literature. If additional information from published literature becomes available at the time of reporting, then the results will be discussed in the context of this new information. The methods of reporting and analysis of results obtained will be done as already described in this protocol and will be further detailed in the statistical analysis plan (SAP).

Description of characteristics of HCPs with desirable/undesirable responses

The charactertistics of HCPs with desirable and undesirable responses to questions related to each outcome will be described using all available and relevant participant information collected in the survey (i.e. region, HCP profession, gender, age range, duration of practice, type of setting, years of professional experience and experience with STAMARIL®). This will be further detailed in the SAP.

Description of characteristics of vaccinees with desirable/undesirable responses

The characteristics of vaccinees with desirable and undesirable responses to questions related to each outcome will be described using all available and relevant participant information collected

in the survey (i.e., age range, region, gender, and education level). This will be further detailed in the SAP.

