6.2 Assessment of success (Vaccinee questionnaire)

Objectives	Questions	Is the question included in the assessment of success? (Yes/No)	Definition of desirably/correctly answered question	Assessment of success
	Q5. Please select the option that best describes			
	your experience with the Patient information Leaflet for the yellow fever vaccine	Yes	Question completed desirably [1 point 1 or 2 is desirable]	A vaccinee is considered successful for receipt of
Awareness of STAMARIL® PIL (2 questions)	Q6. Please provide any additional comment you may have on the Patient Information Leaflet for the yellow fever vaccine	No	Complementary question	STAMARIL® PIL information when he/she receives the yellow fever pre-vaccination checklist. Success for receipt if ≥80% of vaccinees are successful.

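### PIL receipt has two conflicting success cut-offs (>80% and ≥80%), and the 80% verdict ignores the planned confidence interval even if the minimum sample is missed

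*Protocol*

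**What the plan says.** **Threshold.** For PIL receipt, Table 1 (Protocol section 8) states: "If >80% of vaccinees are successful". Annex 6.2 states: "Success for receipt if ≥80% of vaccinees are successful". All four HCP indicators in Table 1 use ≥80%, as do the HCP objectives in Annex 6.1 that give a cut-off.

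**Role of the threshold.** Section 9.7.1 says: "A threshold of 80% successful HCPs or vaccinees on each of the primary outcomes would be considered appropriate for assessing the effectiveness of an aRMM". The rule compares an observed proportion with 80%. The same section calls the threshold subjective.

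**Sample size.** The Abstract says "a minimum sample size of 200 HCPs (a 7% precision) and 150 vaccinees (an 8% precision) will be targeted", at an assumed proportion of 50%. If the minimum is missed within the allocated fieldwork, "the data collection will then be stopped and the study report will be written and submitted based on the analysis of all available data".

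**Reporting.** The Abstract and section 9.7 say "Success indicators by objectives will be presented separately for HCPs and vaccinees", without any condition on the number of respondents. They also say "Wilson CI of 95% will be evaluated on the overall result". Neither they, Table 1, section 9.7.1 nor Annex 6 links that interval to the success rule.

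**The concern.** There are two linked problems in a rule that the protocol itself fixes.

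First, the cut-off for the sole vaccinee objective is written in two incompatible ways. The difference matters only when the observed proportion is exactly 80%. In raw counts that needs n to be a multiple of 5, which includes both the minimum (150) and the goal (300).

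Second, the verdict depends on the point estimate alone. Near the planned sample this is tolerable; well below it, the verdict is often wrong when true receipt is moderately below or above 80%. The protocol's own figures make a vaccinee shortfall plausible, and the vaccinee conclusion sent to health authorities rests on this one indicator.

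**Working it through.** **1. The plan's own sample size.** Section 9.5.1 uses n = P(1−P)·1.96²/e². With P = 0.5:
- e = 0.08: 0.25 × 3.8416 / 0.0064 = 150.1 (stated 150).
- e = 0.07: 0.25 × 3.8416 / 0.0049 = 196.0 (stated 200).
- e = 0.057: 0.25 × 3.8416 / 0.003249 = 295.6 (stated about 300).

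The stated sizes reproduce.

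**2. The two thresholds side by side.** At n = 150, 80% is exactly 120.
- ≥80% (Annex 6.2): success needs 120 or more, so 120/150 passes.
- >80% (Table 1): success needs 121 or more, so 120/150 fails.

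If true receipt is 80%, the chance of success at n = 150 is 0.549 under the first rule and 0.467 under the second. The gap of 0.08 is the chance of observing exactly 120. The strict sign is unlikely to come from the PDF conversion, because ≥ is printed correctly for the HCP knowledge indicator in the same part of Table 1.

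**3. How many vaccinees are plausible.**
- Section 5: 9 completed questionnaires between 16 March and 24 May 2023 (69 days, 9.86 weeks), before the questionnaire was shortened and the honorarium added. Assuming no change in rate, 9/9.86 × 24 ≈ 22 by week 24.
- Table 3, 12 weeks, 2020 volumes: 18 (10% response) to 37 (20% response).
- Table 3, 12 weeks, 2019 volumes: 87 to 174.
- Doubling for 24 weeks gives 36 to 74, or 174 to 348. This is optimistic, since a footnote to Table 3 names March to May as the likely peak.

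**4. Error rates of the point-estimate rule.** Let X be the number of vaccinees with a desirable answer, X ~ Binomial(n, p), with responses assumed independent. Success requires X ≥ r, where r is 0.8n rounded up.

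| n | r | P(success), p = 0.70 | P(success), p = 0.75 | P(failure), p = 0.85 | P(failure), p = 0.90 |
|---|---|---|---|---|---|
| 18 | 15 | 16.5% | 30.6% | 28.0% | 9.8% |
| 37 | 30 | 9.5% | 25.9% | 18.1% | 2.7% |
| 150 | 120 | 0.4% | 9.1% | 3.8% | 0.01% |

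For 18 and 37 the two thresholds give the same r, so this part does not depend on which sign is right.

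**5. What the planned interval would show.** Wilson 95% intervals for a result that just meets ≥80%:
- 15/18 = 83.3%: 60.8% to 94.2%.
- 30/37 = 81.1%: 65.8% to 90.5%.
- 120/150 = 80.0%: 72.9% to 85.6%.

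All three include 80%, so none by itself separates success from failure.

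**The case against.** **The protocol does respond to a shortfall.** Fieldwork may run to 24 weeks (9.5.2, 9.6.1). Vaccinees may be recruited through HCPs outside the HCP survey (9.2.4.2), the HCP cap per centre may rise from 3 to 5 (9.2.4.1), and a feasibility assessment can adjust the target (9.5.2). This stands. A reader might infer that missing the minimum has no consequence at all, and that would be wrong; what is absent is any consequence for the verdict.

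**Collection does not stop early.** It ends when the allocated fieldwork time expires, and section 9.7.3 plans no early analysis. A reader might infer a premature or outcome-driven stop; the text gives no ground for it.

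**Nine is not the expected final sample.** It is an interim count under the superseded design. Treating it as the end point would require no further completions, and the 2019 column of Table 3 reaches 174. A verdict on a handful of vaccinees is not supported as the expected outcome.

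**The analysis is descriptive and an interval will be available.** True, and the statistical analysis plan may add detail. But the success rule is fixed in the protocol, and a descriptive label does not prevent success or failure from being declared. The protocol never states outright that a verdict is issued on a short sample. That is an inference from unconditional indicators together with the all-available-data rule.

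**True receipt may be well above 80%.** Section 9.5.1 cites 90.7% of centres routinely supplying the leaflet, a centre-level proxy. At 90% the failure rate is 2.7% at n = 37, so the rule does far better there. The error rates above apply when true receipt is nearer 80%.

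**A special rule below 150 would be incoherent.** If the interval counted only below the minimum, 128/149 (85.9%, Wilson 79.4% to 90.6%) would be inconclusive while 120/150 stayed a success. This stands, and the fix therefore applies at every n.

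**Conclusion.** The contradiction between Table 1 and Annex 6.2 is certain and affects the decision rule for the only vaccinee objective. It bites only at exactly 80%, which has a probability of about 8% at n = 150 if true receipt is 80%.

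The second part holds as a conditional weakness. If the minimum is still missed after the extension and the added recruitment routes, the 80% point-estimate verdict applies unchanged. At 18 to 37 vaccinees its error rates are roughly 25 to 43 times those at 150 if true receipt is 70%, and 5 to 7 times if it is 85%. This is plausible for vaccinees but not certain; the documents show no comparable recruitment shortfall for HCPs.

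The figures assume independent responses. Section 9.2.4.2 allows up to 10 vaccinees per centre, and receipt probably depends on centre practice, so the real uncertainty may be larger.

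**What to change.** 1. State one threshold, ≥80% as for the HCP indicators, in both Table 1 and Annex 6.2.
2. In section 9.7.1 and Annex 6, for both surveys and at every sample size, report each success indicator with its n and Wilson 95% interval, and say whether the interval includes 80%. Call the verdict inconclusive when it does. Use no separate rule below the minimum.
3. Add to the Abstract (Study size) and section 9.5 that the report will note when the planned minimum precision was not reached.

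These are wording changes, since the interval is already planned. The cost is fewer clear verdicts. At n = 37 a clear success needs 35/37; if true receipt is 90%, 73% of such surveys would be inconclusive. At n = 150 results from 111 to 129 (74% to 86%) would be inconclusive. That happens 7% of the time if true receipt is 90%, but 67% of the time if it is 85%. The sponsor should accept this knowingly.
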